4.3 Exploratory objective

1. To study the change in exploratory biomarkers between the 2 groups
 - Endothelial function based biomarkers
 - Stress based biomarkers
 - Inflammatory biomarkers
 - Hormones, Vitamins and minerals
2. To study the incidence of hypertension mediated organ damage (brain, heart, kidney, artery, eyes)

5. Study design: Multi centric, open label, parallel arm randomized controlled trial

[figure not shown]

Figure-1 Study design

Study period: The total study period will be for approximately 3 years as follows:

Run in period: 2-3 weeks

Intervention period: 2 year

Passive Follow up: 1 year

After screening, all eligible patients will have a mandatory 2-3 weeks run-in period with existing therapy (standard care) for stabilization of blood pressure and for baseline continuous glucose monitoring. Patients with blood pressure >180/110 mm Hg at the end of 3 weeks run-in period will be considered as screen failure.

Number of groups:

Group A (Standard care arm): Will receive medications for hypertension along with lifestyle modifications as per existing guidelines

Group B (Intervention arm): Will receive Twin Precision Treatment along with standard care

6. Eligibility criteria

Inclusion criteria

1. Patients with diagnosis of primary hypertension (either adequately controlled or inadequately controlled with blood pressure \leq 180/110 mm Hg); both treatment naive & on treatment (includes monotherapy or multiple drugs)
2. Age 18 years and above
3. Of either gender
4. Willing to follow study specific activities and able to handle smartphone

Exclusion criteria

Patients with the following criteria will be excluded.

1. Uncontrolled hypertension ($>$ 180/110 mm of Hg) or history of hypertensive emergency requiring admission
2. Hypertension due to secondary causes
3. History of Diabetes mellitus (when either of the following criteria is met: on medications to control blood sugar or FBS $>$ 126 mg/dl; RBS $>$ 200 mg/dl; HbA1c \geq 6.5)
4. Symptomatic heart failure or EF $<$ 40%
5. Chronic kidney disease (eGFR less than 60 ml/min/1.73 m²) or history of any major renal anomalies like unilateral kidney, polycystic kidney
6. Any major cardiovascular event in the last 6 months (such as MI, stroke, TIA)
7. Hypertensive Retinopathy (grade 3 and above)
8. Weight loss more than 5% in 3 months
9. Arm circumference too large or small to allow accurate BP measurement with available devices

- b. Medication history for intake of any excluded medications, medications for conditions included in exclusion criteria
- c. Blood test: Complete blood count, random blood sugar, HbA1c, electrolytes (Calcium and Potassium), liver function test, renal function test, C-Peptide
- d. 2D Echo for heart failure, fundus examination for retinal changes
- e. Urine pregnancy test for women in reproductive age group
- f. Investigations to rule out secondary hypertension (only if clinically indicated)
Doppler USG for renal artery stenosis, calcium score for ASCVD assessment, Urine/plasma metanephrines, urine cortisol, sleep apnoea questionnaire/ polysomnography for sleep apnea

Run in period

After confirming eligibility, the patient will have a 2-3 week run-in period as per standard care for stabilization of blood pressure and for assessing baseline glycaemic control using CGM. Patients not compliant during the run-in period will be excluded from the study.

Baseline assessment

- Baseline assessment will be done after completion of run-in period and before randomization. It includes
- Blood pressure monitoring both in clinic and ambulatory blood pressure
- Vital signs and anthropometric assessment (Height, weight, hip & waist circumference)
- Details of medications taken by the patient
- Quality of life assessment using: SF-36, Perceived stress questionnaire, Treatment satisfaction questionnaire, Montreal Cognitive assessment
- Blood sample for haematology, liver/ renal function test, markers of insulin resistance, HbA1c, inflammatory and other exploratory markers (detailed list included in the schedule of assessment chart)
- Serum renin and aldosterone: In patients receiving potassium-wasting diuretics, the diuretic should be discontinued and potassium supplements should be administered for 1–2 weeks. If hypokalemia persists after supplementation, screening using a serum aldosterone and plasma renin activity should be performed. Ideally, antihypertensives should be stopped before testing, but that is often impractical. Aldosterone receptor antagonists, beta-adrenergic blockers, ACE inhibitors, and angiotensin receptor blockers interfere with testing and should be substituted with other antihypertensives if possible (12).
- Radiological investigations: ECG, Echo with epicardial & pericardial volume, cIMT, USG abdomen with KUB, Renal doppler, and CT Calcium score with pericardial & epicardial thickness.
- Gut microbiome analysis

Twin Health app and sensor-based assessment

Patients will be provided Bluetooth enabled body composition analysis scale, Omron blood pressure monitor, ketone meters, and Garmin wristband for tracking heart rate, footsteps, and sleep. Twin Health app will be installed in their smartphone which captures the data collected from the Bluetooth enabled devices.

7.2 Randomisation and allocation concealment:

Patients will be randomized into either standard care arm or intervention arm using central randomisation in a ratio of 1:2 (standard arm: intervention arm) Block randomisation of variable block size will be used.

Blinding: The study will be an open labelled trial.

7.3 Details of intervention:

7.3.1 Group A (Standard arm):

Will receive standard of care treatment (drugs and lifestyle modifications) as per AHA 2020 International Society of Hypertension- Global Hypertension Practice guidelines.

Counselling on lifestyle modification will be given by an exclusive study coach based on the following considerations

Salt reduction & Healthy diet	
Reduce salt added when preparing foods, and at the table. Avoid or limit consumption of high salt foods such as soy sauce, fast foods and processed food including breads and cereals high in salt
 
Advice will be given to include whole grains, fruits, vegetables, polyunsaturated fats and dairy products and Increase intake of vegetables high in nitrates known to reduce BP, such as leafy vegetables and beetroot. Other beneficial foods and nutrients include those high in magnesium, calcium and potassium such as avocados, nuts, seeds, legumes and tofu
 
Advice to reduce food high in sugar, saturated fat and trans fats,
 
*Dietician will guide the subjects by providing charts on the type of food to consume and the type of food to avoid based on the local availability and above recommendations

Regular physical activity	
All subjects will be in the standard care arm will be advised to perform moderate intensity aerobic exercise (walking, jogging, cycling, yoga, or swimming) for 30 minutes on 5–7 days per week

Weight reduction	
Subjects who are overweight will be motivated to reduce weight to reach an ideal BMI (18.5 to 24.9) or waist hip ratio < 0.5

Moderation of alcohol consumption and smoking cessation	
Counselling will be provided on the importance of cessation of smoking and alcohol consumption. Habitual drinkers will be advised on the moderation of amount and to avoid binge drinking. The recommended daily limit for alcohol consumption is 2 standard drinks for men and 1.5 for women (10 g alcohol/standard drink).

Management of blood pressure in standard care arm

Medication will be started or up titrated if blood pressure is > 140/90 mm Hg and treated to reach target blood pressure

Target blood pressure control will be(10)

Office

- In <65 years < 130/80 mm Hg
- In 65 and above < 140/90 mm Hg

ABPM

- 24 hr average \leq 130 and/or \leq 80
- Day time average \leq 135 and/or \leq 85
- Night time average \leq 120 and/or \leq 70

HBPM \leq 135 and/or \leq 85

Frequency of assessment: For patients in the standard care arm, blood pressure will be assessed monthly after initiation or change in antihypertensive medication until target blood pressure is reached. Subsequently blood pressure will be monitored every 3 monthly.

Standard care home based BP monitoring: Self-measured BP monitoring be based on 2 measurements taken at least 1 minute apart in the morning and evening (ie, 4 readings per day) optimally for 7 days (ie, 28 readings total) with a minimum of 3 days (ie, 12 readings total). For each monitoring period, the average of all SBP and DBP readings should be obtained to assess BP. If the first day's readings are excluded, the preferred and minimum periods of monitoring should be 8 and 4 days, respectively. (9)

Standard care Office based BP monitoring:y 2–3 office visits at 1–4-week intervals. At each visit take 3 measurements with 1 min between them. Calculate the average of the last 2 measurements. If BP of first reading is <130/85 mmHg no further measurement is required.(10)

Stepwise approach for use of antihypertensive medications

Consider monotherapy in low risk grade 1 hypertension or in very old (> 80 yrs).

Category	Systolic		Diastolic
Normal BP	<130	and	<85
High normal BP	130-139	and/or	85-89
Grade 1 hypertension	140-159	and/or	90-99

Grade 2 hypertension	≥ 160	and/or	≥ 100
----------------------	-------	--------	-------

Table-1 Grades of hypertension

Classification of hypertension risk based on risk factors, end organ damage. (Table-2)

Risk factors/ Hypertension mediated organ damage	High normal blood pressure	Grade 1 hypertension	Grade 2 hypertension
No other risk factors	Low	Low	Moderate/high
1 or 2 risk factors	Low	Moderate	High
≥ 3 risk factors	Low/moderate	High	High
HMOD, CKD grade 3, diabete, CVD	High	High	High

Stepwise approach will be followed for adding antihypertensive medications as follows at each visit. (Table- 3)

Step-1 Dual low dose combination	A+C
Step-2 Dual full dose combination	A+C
Step-3 Triple combination	A+C+D
Step-4 (Resistant hypertension) Triple combination + spironolactone or other drug	A+C+D Add spironolactone

A - ACE inhibitor / ARB

C - Calcium channel blocker

D - Diuretics

Supportive references: A+C, Spironolactone, Alpha blocker, C+D

Alternatives include: Amiloride, Doxazosin, Eplerenone, Clonidine or beta-blocker

7.3.2 Group B (Intervention arm):

Will receive Twin Precision nutrition along with standard of care medications for hypertension

Details of Twin Precision Treatment (TPT)

Patients randomized to the intervention group will follow the medicine, exercise, sleep and nutritional syntax of the Twin Precision Treatment program.

Twin Health platform and sensors

The Twin Health platform uses a Whole Body Digital Twin, powered by artificial intelligence and Internet of Things technology, to precisely understand the metabolic impairment in the patient's body, which is unique to the patient. The platform collects data from body sensors and a mobile app to track and analyze the body's health signals in order to personalize patients' treatment.

The Digital Twin precisely understands metabolic dysfunction by monitoring and correlating up to 3000 health data points collected each day through sensors and by integrating with the historical and ongoing patient health data. This is done by providing blood screens and health sensors including a CGM patch, sensor watch, wireless BP meter, BHB meter and body composition scale. The platform then recommends the precision treatment needed to heal the metabolism. The precise nutrition activity and sleep recommendations are presented in the Twin mobile app, which also provides the daily health progress of the patient from day 1.

Patients enrolled in TPT according to the eligibility criteria will be analyzed retrospectively. TPT is an outpatient program. During TPT enrolment, complete information on medical history, family history related to chronic conditions, weight, height and current medication details will be captured.

Health coach: Each patient is paired with a health coach who works with the patient one-on-one to support the TPT. Upon receiving the blood test report, Twin mobile app installation, and sensor activation, the precision nutrition overview will be provided by the health coach. The sensor activation includes synchronizing the beta-hydroxybutyrate meter, body composition scale, wireless blood pressure meter and sensor watch to the Twin mobile app which was downloaded to the patient's mobile phone. As needed, the patients will be advised to perform routines of measuring beta-hydroxybutyrate (BHB) using the Ketone meter kit, measuring blood pressure using the digital Bluetooth-enabled blood pressure meter Omron 7316T, and measuring body composition parameters like weight, visceral fat, etc, using the Omron HBF 222T Bluetooth Smart Scale. Patients will be asked to wear a sensor watch (Garmin watch) to continuously record sleep parameters, heart rate, step count and other fitness parameters.

Continuous glucose monitoring (Ambulatory Glucose Profile, AGP) will be performed as needed using an FDA approved CGM patch which is integrated into the TPT web-based software.

Patients will also be asked to record their food intake and other useful markers on the Twin mobile app using voice or manual log.

Use of Machine learning

Machine learning (ML), a subtype of artificial intelligence, will use the data points that will be captured to learn what drives the glucose response to specific foods for each participant. Factors found to be involved in glycaemic response will be analysed for each participant. Participants will then be provided with a set of specific food recommendations in order to avoid glucose spikes. Using continuous glucose monitor (CGM) data, participant blood glucose values will be predicted using machine learning algorithms and data fusion techniques.

Each food item within every meal will be logged along with its weight by selecting it from a database of more than 2000 foods with nutritional values based on the USDA database and other sources that were further improved and expanded with additional items from certified sources.

The machine learning algorithm is devised to integrate these multi-dimensional data and accurately predict personalized glucose response. Dietary intake is a central determinant of blood glucose levels, and thus, in order to achieve normal glucose levels, it is imperative to make food choices that induce normal postprandial (postmeal) glycemic responses. Thus, the platform will suggest the right food to the right patient.

Meal plan

Depending on the likes and dislikes of the patient, the Twin platform will recommend a meal plan that is balanced across macro, micro and biota nutrients to reduce glucotoxicity and lipotoxicity, which helps in healing inflammation, fatty liver and damaged pancreas. This precise management of nutrition, activity and sleep ensures that the average blood glucose of the day will be consistently maintained within the optimal range. By continuously offering precision nutrition, precision sleep and precision activity recommendations, the food tolerance of the body will gradually improve. Patients will also be provided supplements to ensure sufficient micronutrients are consumed. Nutritional, activity and sleep counselling will be provided by trained health coaches through the app and via telephone.

General strategy for diet modification in Twin Precision treatment will be

- To avoid sugar(No added sugar); avoid refined oil, trans fats and substitute with healthy fats(Butter, Ghee, Olive oil, coconut oil, Sesame Oil, and Mustard oil)
- Reduce the frequency of feeding(Avoid snacks and reduce feeding window)
- Apply meal syntax vegetables first, then proteins and then carbs
- Add Non starchy vegetables in plenty(At Least five- seven servings); Adequate protein intake(1-2gms per kg of lean body weight); Green foods and supplements

Medication for blood pressure management

Blood pressure of the participants will be monitored periodically using home based, clinic based, and ambulatory blood pressure monitoring. Dose reduction or withdrawal of

antihypertensive drugs will be attempted when the patient reaches the target blood pressure.

Antihypertensive withdrawal protocol

Dose reduction or withdrawal of antihypertensive drugs will be considered when the patient reaches the target blood pressure. The dose reduction is in accordance with the protocol described by Nelson et al. i.e half dose reduction at weekly intervals with weekly assessment until the lowest dose is reached followed by withdrawal. The period of withdrawal will range from 2 weeks to 4 weeks.

Target blood pressure for our study will be considered as 130/80 mm Hg for young individuals and 140/90 mm Hg for elderly (65 and above) -2020 International Society for Hypertension Global Hypertension Practice Guidelines

Table-4 Antihypertensive medicines escalation and de-escalation protocol

Tier number	Medicines	Initial condition on enrolment	Reduction condition	Increase conditions
Tier 0	No medicine	Initial no medicine & BP < 160/100 mm Hg		Move to Tier 1, if (5d-BP > 135/85) & (after staying in this tier for 5 days)
Tier 1	Monotherapy (A)	Monotherapy	Move to Tier 0, if ((1d-BP < 135/85 for 7 consecutive days) II (1d-BP < 90/60 for 3 consecutive days) II (Symptoms of Hypotension like Postural Giddiness)) && (EOD-)	Move to Tier 2, if (5d-BP > 135/85) && (after staying in this tier for 5 days)
Tier 2	Dual low dose combination (A+C)	Dual low dose combination	Move to Tier 1, if ((1d-BP < 135/85 for 7 consecutive days) II (1d-BP < 90/60 for 3 consecutive days) II (Symptoms of Hypotension like Postural Giddiness))	Move to Tier 3, if (5d-BP > 135/85) && (after staying in this tier for 5 days)

Tier 3	Dual full dose combination (A+C)	Dual full dose combination/ Triple combination/ Triple combination + spironolactone or Alpha blocker	Move to Tier 2, if ((1d-BP < 135/85 for 7 consecutive days) II (1d-BP < 90/60 for 3 consecutive days) II (Symptoms of Hypotension like Postural Giddiness))	Move to Tier 4, if (5d-BP > 135/85) && (after staying in this tier for 5 days)
Tier 4	Triple combination (A+C+B/ D/ Alpha blocker)	Triple combination/ Triple combination + spironolactone or Alpha blocker	Move to Tier 3, if ((1d-BP < 135/85 for 7 consecutive days) II (1d-BP < 90/60 for 3 consecutive days) II (Symptoms of Hypotension like Postural Giddiness))	Consider manual change of medication or withdraw

A= ACE inhibitor or ARB

C = Calcium channel blocker

B = Beta blocker

D = Diuretics

Note:

- EOD (End organ damage) + =
1. LVH present
 2. Albuminuria
 3. Evidence of Heart failure
 - A. Low ejection fraction
 - B. High pro-BNP
 - C. Clinical features
 4. Hypertensive retinopathy

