9.1 Primary endpoint

1. Primary outcome will be change in blood pressure as measured by ambulatory blood pressure monitoring at the end of 1 year
2. Primary outcome will be a change in blood pressure as measured in the clinic at the end of 1 year

Ambulatory blood pressure monitoring

Measurements will include mean 24h systolic and diastolic pressures, and daytime values (measured every 30 min from 07:00 am to 10:00 pm) and night-time values (measured every 60 min from 10:00 pm to 07:00 am). Only ambulatory BP recordings with a minimum of 70% measurements will be considered as successful.

In Clinic or office blood pressure: Average of 3 readings measured in the morning with 1 min gap at baseline and end of the study will be considered. Procedure for measurement of blood pressure is detailed under section 6.5 Blood pressure monitoring

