9.2 Secondary outcome

Blood pressure and antihypertensive medication related

1. **Change in blood pressure (Clinical and ambulatory blood pressure)** from baseline to 6 months and 2 year. Ambulatory and clinic blood pressure monitoring will be done as mentioned in the primary endpoint.
2. **Adequate control of blood pressure** as measured by ambulatory blood pressure monitoring at 1 year and 2 years

Criteria for adequate control of blood pressure is

- In <65 years < 130/80 mm Hg
- In 65 and above < 140/90 mm Hg

3. Number of antihypertensive medications at 6 months, 1 year and 2 years

Among those with adequate control, the number of antihypertensive medications will be calculated at baseline (after run in period) and subsequently every 3 months. Combination pills containing more than one group (of antihypertensive medications) will be considered based on the number of groups. Example: Lotrel which is a combination of Amlodipine and benazepril will be considered as 2 drugs. Further each drug will be categorized as high dose or low dose.

Table-5 for doses of commonly used antihypertensive medications

Drug name	Dose 1	Dose 2	Dose 3	Dose 4
Losartan	25 mg	50 mg		
Telmisartan	20 mg	40 mg	80 mg	
Olmesartan	5 mg	20 mg	40 mg	
Candesartan	16 mg	32 mg		
Captopril	12.5 mg	25 mg	50 mg	100 mg
Enalapril	5 mg	10 mg	20 mg	40 mg
Lisinopril	5 mg	10 mg	20 mg	40 mg
Ramipril	1.25 mg	2.5 mg	5 mg	
Hydrochlorothiazide	12.5 mg	25 mg	50 mg	100 mg

Chlorthalidone	25 mg	50 mg	100 mg	
Indapamide	1.25 mg	2.5 mg	5 mg	
Frusemide	20 mg	40 mg		
Prazosin	1 mg	2.5 mg	5 mg	
Terazosin	1 mg	2 mg	5 mg	
Doxazosin	1 mg	2 mg	4 mg	
Propranolol	10 mg	20 mg	40 mg	
Metoprolol	25 mg	50 mg	100 mg	
Atenolol	50 mg	100 mg		
Bisoprolol	5 mg	10 mg		
Amlodipine	5 mg	10 mg		
Cilnidipine	5 mg	10 mg	20 mg	
Nicardipine	20 mg	40 mg	80 mg	
Nifedipine	30 mg	60 mg	90 mg	
Felodipine	2.5 mg	5 mg	10 mg	

4. Frequency of introduction of new antihypertensive medications or dose increment of existing antihypertensive medications will be noted across both the groups and compared.

Metabolic parameters and biomarkers based

5. Change in metabolic parameters

- Will include anthropometric assessment (Height, Weight, BMI, waist circumference, Waist hip ratio, visceral fat), lipid profile including lipoprotein (a), apolipoprotein - A1, apolipoprotein - B, insulin resistance (measured by HOMA- IR) every 3 months till end of study

6. Change in cardiac and renal biomarkers

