12.1. Sample size calculation

Sample size is calculated based on the expected difference in mean reduction in systolic blood pressure at the end of 1 year between the 2 groups.

Based on an expected difference in mean reduction SBP from baseline to 1 year between the 2 groups as 5 mm Hg and standard deviation of 13 mm Hg, with power 80% and 5% alpha error, having 1:2 allocation ratio the estimated sample size is **83 in standard care arm and 166 in the intervention arm**. Accounting for an additional 20% drop out the final numbers are **104 in standard care and 208 in the intervention arm**.

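### Only Group B has a written drug step-down rule, yet the outcome meant to show drug reduction is limited to controlled patients and cannot be read beside the primary BP difference

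*Protocol*

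**What the plan says.** **Primary outcomes.** Protocol 9.1 sets two, both on BP alone: "Primary outcome will be change in blood pressure as measured by ambulatory blood pressure monitoring at the end of 1 year" and "Primary outcome will be a change in blood pressure as measured in the clinic at the end of 1 year". Neither refers to the drugs taken at that time.

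**Group B drugs.** Section 7.3.2 says that reduction or withdrawal of "antihypertensive drugs will be attempted when the patient reaches the target blood pressure". Under its withdrawal protocol it then states: "Dose reduction or withdrawal of antihypertensive drugs will be considered when the patient reaches the target blood pressure". Table 4 gives the mechanism. A patient moves down one tier after seven consecutive days below 135/85 (or with low readings or symptoms), and up one tier if the 5-day value exceeds 135/85. The step from Tier 1 to no drug also requires absence of end organ damage.

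**Group A drugs.** Section 7.3.1 states: "Medication will be started or up titrated if blood pressure is > 140/90 mm Hg and treated to reach target blood pressure". Table 3 then adds drugs stepwise. No reduction rule is written for this arm. Review is monthly until target and 3-monthly afterwards.

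**Drug outcomes.** Section 9.2 item 3 begins: "Among those with adequate control, the number of antihypertensive medications will be calculated at baseline", and continues every 3 months. Objective 3 in 4.2 carries the same restriction. Item 4 counts new drugs and dose increases in both groups.

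**Sample size.** Section 12.1 uses an "expected difference in mean reduction SBP from baseline to 1 year between the 2 groups as 5 mm Hg", with SD 13 mm Hg, 80% power and 5% alpha.

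**The concern.** Group B's rule acts on the quantity that the primary analysis measures. If the programme lowers BP, Table 4 removes drugs, and section 13 accepts that tapering may let BP rise. Some of the benefit can then move from the BP column to the drug column. A small BP difference would be hard to interpret without a drug comparison in the same patients.

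The protocol has a drug-reduction outcome, but it is confined to patients with adequate control. Item 2 of 9.2 defines control by ambulatory BP at 1 and 2 years, so membership is decided after randomisation and depends on both the treatment and the titration rules. The controlled patients in the two arms are no longer comparable groups. The outcome also leaves out any patient whose drugs were cut and whose BP then settled above the control limit. Two things are at stake: a modest BP difference could be misread as weak efficacy, and a drug-reduction claim could rest on a selected subset.

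**Working it through.** **1. The drug rules side by side**

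| | Group A (7.3.1) | Group B (7.3.2, Table 4) |
|---|---|---|
| Step up | above 140/90 | above 135/85 over 5 days |
| Step down | no written rule | below 135/85 for 7 consecutive days |
| Review | monthly, then 3-monthly | tier rules on 1-day and 5-day readings |

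The step-down row tends to raise BP in Group B relative to Group A. The lower step-up threshold and quicker review tend to lower it. The two act in opposite directions, and the document gives nothing from which to net them.

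**2. Who is counted in item 3**

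- Under 65, control means ambulatory BP below 130/80 (9.2 item 2).
- Section 7.3.1 lists 24-hour 130/80 and home 135/85 as parallel targets.
- Section 7.5 uses home readings for titration, and Table 4 steps down below 135/85 and up above it.

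A patient under 65 who has been stepped down until home BP sits near 135/85 is therefore close to the ambulatory control limit. Such a patient may fall outside item 3 although the drug reduction did occur. Item 4 does not fill the gap, since it records increases only.

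**3. The planned sample size**

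Inputs from 12.1: difference 5, SD 13, alpha 5% (two-sided per 12.2), power 80%, ratio 1:2.

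- Normal formula: n(A) = 1.5 × (13 × (1.96 + 0.8416) / 5)² = 79.6, so 80 and 160.
- Two-sample t-test: 80.2, so 81 and 162. The stated 83 and 166 are within 3% of this.
- Dropout: 83 / 0.8 = 103.75, so 104; 166 / 0.8 = 207.5, so 208. Both match.

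The arithmetic is sound. The open point is what the 5 mm Hg stands for.

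**4. Power if the 5 mm Hg is before de-escalation**

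SE = 13 × √(1/83 + 1/166) = 1.748. Power ≈ Φ(d / SE − 1.96). At d = 5 this is Φ(2.861 − 1.96) = Φ(0.901) = 82%; the t-test gives 81%.

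Net difference = 5 − (share of Group B with drugs cut × mm Hg given back per such patient). Neither input is in the protocol, so both are assumptions. With 5 mm Hg given back per patient:

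| Share cut | Mean offset | Net difference | Power at 83/166 |
|---|---|---|---|
| 0% | 0 | 5.0 | 81% |
| 20% | 1.0 | 4.0 | 63% |
| 40% | 2.0 | 3.0 | 40% |
| 50% | 2.5 | 2.5 | 30% |

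With 10 mm Hg per patient, a 20% share gives the same 2.0 offset (0.20 × 10) and 40% power. Patients with no drug at baseline have nothing to cut, so the share depends on the treated fraction, which is not given.

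**The case against.** **The comparison is one of whole strategies.** The synopsis makes individualised medicine part of Twin Precision Treatment, so comparing 1-year BP under each arm's full strategy is coherent. This stands, and it is why the BP primary outcome should stay. It does not remove the need for an unselected drug comparison beside it.

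**The 5 mm Hg may already be net.** Section 12.1 speaks only of the expected difference between groups, and the rationale in section 3 cites BP falls together with fewer drugs. A net reading is at least as natural as a gross one. This stands: a reader might infer that the power calculation ignores de-escalation, but the text does not say so.

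**Part of this is already covered.** The synopsis lists drug requirement without restriction, item 4 covers both groups, objective 3 mentions both groups, and 12.2 leaves regression open. However, 9.2 is where the drug outcome is defined, and it restores the restriction. Item 4 covers only one direction of change.

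**Item 3 might mean control at baseline.** That would avoid the selection problem. But item 2 assesses control at 1 and 2 years, and a baseline restriction would still omit inadequately controlled patients, who are eligible.

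**The step-down may be used less than Table 4 suggests.** Section 7.3.2 says both attempted and considered. Table 4 asks for seven consecutive days, while 7.5.2 schedules home readings on five days a week. Those passages need reconciling, and the amount of attenuation depends on how that is done. Reductions in Group A outside any written rule are also possible. These points limit the size of the effect and do not touch the selection problem in item 3.

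**Conclusion.** The point holds in a limited form. The written rules allow part of a real benefit to appear as fewer drugs, so the primary BP difference can be attenuated. The outcome that should show this is restricted to a subset formed after randomisation. No outcome defined in the protocol compares drug reduction in all randomised patients.

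A reader might go further and infer that a working programme would show no BP difference, or one favouring Group A. The document does not support that. The arms also differ in escalation threshold and review interval, partly in the opposite direction. Any predicted sign depends on inputs the protocol does not give: mm Hg per drug step, the treated share, and how often step-down occurs.

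The power loss is conditional in the same way. If 5 mm Hg is net of de-escalation, the stated sample size stands. If it is gross, an average offset of 1 to 2.5 mm Hg, which is an assumption, takes power from 81% to between 63% and 30%. The absence of a drug-adjusted sensitivity analysis is not a finding, since that can sit in a statistical analysis plan that is not at hand.

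**What to change.** Keep the BP primary outcomes. This point asks for no change to either arm's drug rules.

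1. In 4.2 objective 3 and 9.2 item 3, replace the restriction to controlled patients with a comparison of the change in antihypertensive drug load from baseline to 1 year in all randomised patients. Define drug load as the number of drugs and the Table 5 dose level. State that it is a key secondary outcome to be read jointly with the 1-year BP difference. Keep the controlled-only analysis as supportive.
2. In 12.1, state that the 5 mm Hg is the difference expected after de-escalation. If it is not, restate the power for the net difference and give the assumed offset.

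The cost is a wording change and one more key secondary analysis. Item 3 already plans drug counts every 3 months and a dose category for each drug, but recording must cover every randomised patient, whether controlled or not.
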